Dasiglucagon (ZP4207) is a stable peptide analog of human glucagon, available in a ready-to-use liquid formulation and is in development for the treatment of severe hypoglycemia in insulin dependent patients with diabetes mellitus. Dasiglucagon is a specific and full glucagon receptor agonist designed to mimic the effects of glucagon, having a fast absorption and elimination (minutes). It is a peptide of 29 amino acids, with 7 amino acid substitutions compared to native glucagon. The main purpose of the substitutions is to increase the physical and chemical stability of the glucagon analog compared to marketed glucagon products such as Lilly's Glucagon or GlucaGen®. Dasiglucagon exhibits improved physical and chemical stability and is available in an aqueous solution at neutral pH.²

Five clinical trials have been completed with dasiglucagon: A first human dose trial (ZP4207-14013), a multiple-dose dose-escalation trial (ZP4207-15007) to evaluate the safety, tolerability, pharmacokinetics (PK) and pharmacodynamics (PD) of dasiglucagon, a phase 2 crossover trial to assess the PK and PD of a single dose of an optimized formulation of dasiglucagon administered subcutaneously (SC) in patients with T1DM (ZP4207-15126), and a feasibility trial testing the bionic pancreas with dasiglucagon was completed (ZP4207-16051).² Finally, a crossover trial (ZP4207-16098) assessing PK and PD responses after micro-doses of dasiglucagon administered SC to patients with type 1 diabetes mellitus under euglycemic and hypoglycemic conditions, compared to marketed glucagon, was completed.

Pharmacokinetics and pharmacodynamics of dasiglucagon

The results of the phase 1 and 2 clinical trials confirm dose-proportionality for dasiglucagon PK, which is characterized by a fast absorption with a peak plasma concentration obtained after 35 minutes. Thereafter, the plasma concentration rapidly declines with an average half-life of 28 minutes. The median time to the maximum plasma concentration (C_{max}) was later for dasiglucagon than for GlucaGen® (35 versus 20 minutes). For C_{max} , the results indicated that 0.3 mg dasiglucagon was comparable to 0.5 mg GlucaGen® (90% confidence interval: 0.8167; 1.0068) and 0.6 mg dasiglucagon was comparable to 1.0 mg GlucaGen® (90% confidence interval: 0.8850; 1.1991).² At these dose levels, the total exposures (AUC_{0-inf}) were higher for dasiglucagon compared to GlucaGen®.

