## 6. GENERAL ANALYSIS CONSIDERATIONS

The statistical analyses will be reported using summary tables, listings, and figures (TLFs). The International Council for Harmonisation (ICH) numbering convention will be used for all TLFs. Unless otherwise noted, all statistical testing will be 2-sided and will be performed at the 0.05 significance level. Tests will be declared statistically significant if the calculated  $P$  value is  $\leq 0.05$ .

All data obtained in this trial and documented in the eCRFs will be listed and summarized with statistics or frequency tables as appropriate. In case of termination of the trial, all data collected up to that time point will be included into the analysis.

Continuous variables will be summarized with means, standard deviations, medians, minimums, and maximums and valid cases. Other summaries (eg, quartiles, 5%, 95% intervals) may be used as appropriate. For PK parameters except Tmax, geometric mean and geometric % CV will be calculated.

Categorical variables will be summarized by counts and by percentage of patients in corresponding categories. Percentages for missing values are omitted and do not account for the percent calculation of other categories. Percentages are routinely based on the total category count excluding the missing category if not otherwise mentioned. Percentages showing a rate relative to the total number of patients in this group are given in special tables (eg, adverse event [AE] tables). Footnotes will specify the percent basis in those cases.

All summary tables will be presented by treatment group if possible and also include a total summary column.

Individual patient data obtained from the eCRFs, external vendors, and any derived data will be presented by patient in data listings.

The analyses described in this plan are considered a priori, in that they have been defined prior to breaking the blind.

Any analyses performed subsequent to breaking the blind will be considered post hoc and exploratory. Post hoc analyses will be labeled as such on the output and identified in the CSR.

All analyses and tabulations will be performed using SAS® software Version 9.4 or higher. Pharmacokinetic and pharmacodynamic (PD) analyses will be performed using Phoenix®

WinNonlin® Version 6.4 or higher. Tables, listings, and figures will be presented in ASCII or RTF format.

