## 12. PHARMACOKINETIC ANALYSES

Plasma dasiglucagon and glucagon concentrations will be described and the following parameters are calculated and summarized with descriptive statistics:

PK parameter	PK parameter abbreviation	Calculation
Area under the plasma dasiglucagon or GlucaGen ® concentration versus time curve from 0 to 30 minutes post-dose	AUC 0-30min	Linear trapezoidal rule for the ascending part of the concentration-time curve, logarithmic trapezoidal rule for the descending part.
Area under the plasma dasiglucagon or GlucaGen ® concentration versus time curve	AUC 0-300min	Linear trapezoidal rule for the ascending part of the concentration-time curve, logarithmic trapezoidal rule for the

PK parameter	PK parameter abbreviation	Calculation
from 0 to 300 minutes post-dose		descending part.
Area under the plasma dasiglucagon or GlucaGen ® concentration versus time curve from 0 to infinitely post-dose	AUC 0-inf	(AUC last + C last,obs )/ λ z , where C last,obs is the concentration corresponding to T last (time of last measurable (positive) concentration).
Maximum of all valid plasma dasiglucagon or GlucaGen ® concentration measurements from 0 to 300 minutes post-dose	C max	Taken directly from analytical data, selected from individual concentration data. The time when the first occurrence of C max is taken as T max .
Time to maximum of plasma dasiglucagon or GlucaGen ® concentration measurements	t max	Taken directly from analytical data, selected from individual concentration data
Terminal elimination rate constant of plasma dasiglucagon or GlucaGen ®	λ z	Calculated by linear regression of the terminal linear portion of the log concentration vs. time curve. At least 3 concentrations in the terminal elimination phase will be required to calculate λ z .
Terminal plasma elimination half-life of dasiglucagon or GlucaGen ®	t 1/2	Ln(2)/ λ z
Total body clearance of plasma dasiglucagon or GlucaGen ®	CL/f	Dose/ AUC 0-inf
Volume of distribution of plasma dasiglucagon or GlucaGen ®	V z /f	Dose/ (λ z * AUC 0-inf ) or CL/f/ λ z

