Mean residence time of plasma dasiglucagon or GlucaGen ®	MRT	AUMC inf / AUC 0-inf where AUMC inf is the area under the first moment curve as estimated by WinNonlin.

The PK metrics as listed above will be obtained by non-compartmental analysis using the computer programs Phoenix® WinNonlin® Version 6.4.

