## Appendix B: SAS Programming QC Requirements

### Programmer/Validator Review

#### 1. Program Review

- 1.1. **Program name** follows standard naming conventions and is consistent with other study program names.
- 1.2. **Program header** uses standard template with all relevant information completed.
- 1.3. **Program flow** is logical (ie, header → initialization code → macro variable definitions → format definitions → main body).
- 1.4. **Programmer comments** are included throughout program to describe purpose of individual sections or macros and provide understanding of specific code, if necessary. All comments are clear and up-to-date.
- 1.5. **Hard coding**, if any, is implemented correctly and documented in program header with: date, reason, and reference to sponsor approval. A comment is also inserted at the location of the hard coding.
- 1.6. **SAP derivation rules**, if any, are followed. Significant deviations from mock table or SAP text are documented in the SAS Program Header.
- 1.7. **Permanent intermediate datasets** utilized as source data have either been fully validated elsewhere or are fully validated within the scope of this QC.
- 1.8. **Program runs** properly and output dataset is generated as intended.

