##### 5.3. Listings

- Listing content is as expected (eg, listing includes all enrolled patients, all expected visits)
- Variables directly from source dataset are spot-checked for accuracy and completeness.
- Derived or calculated variables are compared to corresponding source data and manual calculation for at least 2 patients are done.

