**Section 16.2: List of Data Listings**

ICH Listing Number	Listing Title	Comment
16.2	PATIENT DATA LISTINGS	
16.2.1	Discontinued patients	
16.2.1.1	Patient disposition	
16.2.1.2	Trial termination	
16.2.2	Protocol deviations	
16.2.2.1	Patients not fulfilling any inclusion/exclusion criteria	
16.2.3	Patients excluded from the efficacy analysis	
16.2.3.1	Patients Excluded from analysis	
16.2.4	Demographic data	
16.2.4.1	Informed consent and demographics	
16.2.4.2	Baseline characteristics (body measurements)	
16.2.4.3	Diabetes history	
16.2.4.4	Medical history	
16.2.5	Compliance and/or drug concentration data	
16.2.5.1	Visit dates	
16.2.5.2	Randomisation	
16.2.5.3	Insulin administration prior to the hypoglycemia induction procedure	
16.2.5.4	Hypoglycemia induction procedure	
16.2.5.5	Study drug administration	
16.2.5.6	Post-treatment rescue glucose infusion	
16.2.5.7	Plasma dasiglucagon/GlucaGen sampling and concentrations	
16.2.5.8	Plasma dasiglucagon/GlucaGen pharmacokinetic metrics	
16.2.6	Individual efficacy response data	
16.2.6.1	Plasma glucose sampling and concentrations	

ICH Listing Number	Listing Title	Comment
16.2.6.2	Plasma glucose pharmacodynamic metrics	
16.2.6.3	Time to plasma glucose recovery	Derived including derived parameters
16.2.7	Adverse events listings	
16.2.7.1	Adverse events - CRF entries	
16.2.7.2	Adverse events - MedDRA coding	
16.2.7.3	Adverse Event of Special Interest - additional details	
16.2.7.4	Death and serious adverse events	
16.2.7.5	Adverse events – leading to withdrawal from study	
16.2.7.6	Adverse events – patients with positive ADA result	
16.2.7.7	Adverse events - plasma glucose measurements in case of hypoglycemia	
16.2.8	Listing of individual laboratory measurements by patient, when required by regulatory authorities	
16.2.8.1	Hematology	incl. derived data CFB
16.2.8.2	Biochemistry	incl. derived data CFB
16.2.8.3	Coagulation	incl. derived data CFB
16.2.8.4	Urinalysis	
16.2.8.5	Pregnancy test	
16.2.8.6	Alcohol breath test	
16.2.9	Other data	
16.2.9.1	Vital signs	
16.2.9.2	Physical examination	
16.2.9.3	Electrocardiogram	incl. derived data CFB
16.2.9.4	Concomitant medication and current diabetes treatment	
16.2.9.5	Local tolerability	

ICH Listing Number	Listing Title	Comment
16.2.9.6	Immunogenicity results	

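### The SAP's printed formula for AUC0-inf has a misplaced bracket and is dimensionally invalid; AUC0-inf, CL/f, Vz/f and MRT would be wrong if it were programmed or used for checking

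*SAP*

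**What the plan says.** The parameter table in SAP section 12 has a calculation column. For AUC0-inf the entry opens a bracket and continues "AUC last + C last,obs )/ λ z", with C_last,obs explained as the concentration at the last time with a measurable value. Four other rows of the table bear on this:

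- t½ is ln(2)/λz.
- CL/f is dose divided by AUC0-inf.
- Vz/f is dose divided by the product of λz and AUC0-inf, or equivalently CL/f divided by λz.
- MRT is AUMCinf divided by AUC0-inf, where AUMCinf "is the area under the first moment curve as estimated by WinNonlin".

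On software, the text under the table says: "The PK metrics as listed above will be obtained by non-compartmental analysis using the computer programs", naming Phoenix WinNonlin. SAP section 6 agrees: "Pharmacokinetic and pharmacodynamic (PD) analyses will be performed using Phoenix".

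On checking, SAP Appendix B item 1.6 states that SAP derivation rules, "if any, are followed. Significant deviations from mock table or SAP text are documented in the SAS Program Header". Item 5.3, on listings, states: "Derived or calculated variables are compared to corresponding source data and manual calculation for at least 2 patients are done". Listing 16.2.5.8 in Appendix C is "Plasma dasiglucagon/GlucaGen pharmacokinetic metrics".

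Protocol section 10.1.5 names AUC0-inf among the PK endpoints but gives no formula. The cell in SAP section 12 is therefore the only written rule.

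**The concern.** The standard extrapolation adds to AUC_last a tail equal to C_last,obs/λz. Only the last concentration is divided by λz. As printed, the bracket encloses both terms, so AUC_last is divided by λz as well. The sum inside the bracket mixes an area with a concentration, and the result is not an area.

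The PK profile in children is a stated secondary objective, and CL/f, Vz/f and MRT inherit whatever is done for AUC0-inf. The SAP describes itself as the source of the specific rules for the analysis and says departures from it are to be documented in the study report. A programmer or checker who took the cell at face value would produce wrong values, or would report a conflict with correct WinNonlin output. One who silently substituted the right formula would leave the record showing a rule that was not followed.

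**Working it through.** There is no stated figure to reproduce, because no sample size, power or alpha figure depends on this formula. The check is one of dimensions, followed by an illustration of size.

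**Inputs**

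- The printed rule and the definition of C_last,obs: SAP section 12.
- λz has dimension 1/time, because the same table gives t½ = ln(2)/λz.
- Half-life: Protocol section 5.1 reports for adults that "the plasma concentration rapidly declines with an average half-life of 28 minutes". Protocol section 5.2 expects a shorter half-life in children but gives no figure, so 15 to 40 minutes is an assumed range.
- PK sampling times: 0, 10, 20, 30, 40, 60, 90, 140, 220 and 300 minutes (SAP section 12.1).
- AUC rule: linear on the ascending part, logarithmic on the descending part (SAP section 12).

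**Step 1: dimensions**

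- AUC_last is concentration × time and C_last,obs is concentration, so they cannot be added.
- Dividing the bracket by λz turns the AUC_last term into concentration × time². Only the C_last,obs term comes out as concentration × time.
- AUC_last + C_last,obs/λz is concentration × time in both terms.

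This step needs no PK model and no half-life.

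**Step 2: size of the error**

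Both versions contain C_last,obs/λz, so numerically

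printed − correct = AUC_last × (1/λz − 1).

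The multiplier on AUC_last is 1/λz = t½/ln(2), and its value depends on the time unit. For 28 minutes: 28/0.6931 = 40.40 in minutes, and 40.40/60 = 0.673 in hours. The ratio columns below come from a one-compartment, first-order absorption curve at the protocol sampling times, with target tmax of 20 or 35 minutes (35 minutes only at t½ = 15, where the absorption rate was set to 1.05 times the elimination rate).

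| t½ (min) | 1/λz, minutes | 1/λz, hours | Printed/correct AUC0-inf, minutes | Printed/correct, hours | CL/f, Vz/f, MRT factor, minutes | Same, hours |
|---|---|---|---|---|---|---|
| 15 | 21.64 | 0.361 | 21.6 | 0.361 | 0.046 | 2.77 |
| 28 | 40.40 | 0.673 | 40.3–40.4 | 0.674 | 0.025 | 1.48 |
| 40 | 57.71 | 0.962 | 57.2–57.3 | 0.962 | 0.017 | 1.04 |

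The true tail beyond 300 minutes in these profiles is 0.001%, 0.09–0.23% and 0.67–0.93% of AUC0-inf respectively. A correct AUC0-inf should therefore be within 1% of AUC0-300min.

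**Step 3: a worked profile with fitted λz**

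This uses a half-life of 28 minutes, tmax of 35 minutes, and λz from log-linear regression on the last three points: 1.373 per hour, or 1.373/60 = 0.02288 per minute. Concentration units are arbitrary.

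- Minutes: AUC_last = 39,640.2, C_last = 2.2152. Correct: 39,640.2 + 2.2152/0.02288 = 39,737. Printed: (39,640.2 + 2.2152)/0.02288 ≈ 1,732,400. Ratio 43.6.
- Hours: AUC_last = 660.67, C_last = 2.2152. Correct: 660.67 + 2.2152/1.373 = 662.3. Printed: (660.67 + 2.2152)/1.373 = 482.8. Ratio 0.73.

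The two correct values are the same quantity (39,737/60 = 662.3). The two printed values are not. CL/f and Vz/f change by 1/43.6 = 0.023 in minutes and 1/0.729 = 1.37 in hours. MRT, correct at 71.3 minutes or 1.19 hours, would come out as 1.64 or 1.63. The ratio is 43.6 here rather than 40.4 because the fitted λz is slightly below ln(2)/28.

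**Step 4: sensitivity**

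With half-lives of 15 to 60 minutes, tmax of 15 to 35 minutes, and the last measurable sample at 300 or 140 minutes, the AUC0-inf ratio runs from about 22 to 83 in minutes and from 0.36 to 1.43 in hours. In hours the multiplier passes 1 at t½ = 60 × ln(2) = 41.6 minutes, so the direction of the error can reverse.

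**The case against.** The strongest reply is that this is a misprint that no one will execute. The SAP says twice that PK metrics come from WinNonlin, and where it wants SAS for a comparable quantity, AUE0-30min in section 13, it says so. Appendix B concerns SAS programming, and item 1.6 refers to a SAS program header, which a WinNonlin run does not have. The source data for the PK listing could be the WinNonlin output itself, so hand recalculation from the section 12 cell is an inference. If someone did recalculate, the conflict would expose the misprint without corrupting any result. In hours, over the assumed 15 to 40 minute range with sampling to 300 minutes, the printed rule puts AUC0-inf below AUC0-300min, which is impossible and should be noticed. MRT goes wrong only if WinNonlin's AUMCinf is divided by a separately computed AUC0-inf.

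Most of this stands as a limit on consequences. The documents do not show that any reported value will be wrong, and the MRT condition is a fair qualification. The minute-based multipliers should not be read as the expected error: the one time unit shown for a PK metric, Tmax in the shell for Table 14.4.1.2, is hours, although that is a reporting unit and does not settle the calculation unit. The upper part of the assumed half-life range also exceeds the adult figure, although children are expected to have shorter half-lives, and no half-life is given for GlucaGen.

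None of it makes the printed rule correct. Item 5.3 makes no exception for PK listings, and a reader has no other formula to turn to. In hours the distortion of CL/f and Vz/f is 1.04 to 2.8 times over the assumed range, which is harder to spot by eye than a factor of 40.

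**Conclusion.** The concern holds. The AUC0-inf rule in SAP section 12 is wrong as written, on dimensional grounds alone. Four of the ten PK metrics depend on it: AUC0-inf, CL/f and Vz/f directly, and MRT through its denominator. Applied literally at a 28-minute half-life, it would multiply AUC_last by 40.4 in minutes or 0.67 in hours. Over an assumed 15 to 40 minutes, CL/f, Vz/f and MRT would be about 22 to 57 times too small in minutes, or 1.04 to 2.8 times too large in hours. These sizes rest on adult data, an assumed range and a one-compartment profile.

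The defect is in the specification. PK endpoints are descriptive and outside the testing hierarchy in SAP section 10.7. The primary endpoint, power, type I error, AUC0-30min, AUC0-300min, Cmax, tmax, λz and t½ are unaffected. Both brackets are present in the text as read, so a PDF reading fault is unlikely, though the original page can confirm this. It should be corrected because it is the only written rule for a parameter serving a secondary objective.

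**What to change.** Replace the calculation entry for AUC0-inf in SAP section 12 with: AUC0-inf = AUC_last + (C_last,obs / λz). Leave the CL/f, Vz/f and MRT rows as they are, since they are right once AUC0-inf is right. State one time unit for λz and the areas, and confirm that the WinNonlin setting and any manual recalculation for Listing 16.2.5.8 use this formula and that unit. The cost is a one-line correction and a short check, with no new data or analysis.

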## 12.1 Data Handling

Plasma dasiglucagon and GlucaGen® are determined at pre-dose, and at 10, 20, 30, 40, 60, 90, 140, 220, and 300 minutes after dosing. The actual time of blood sampling should not deviate from the nominal time by more than ±1 minute between t=5 minutes and t=90 minutes, ±5

minutes between  $t=140$  minutes and  $t=240$  minutes. Pre-dose is defined as within 2 minutes prior to dosing).

### Summary tables and figures for plasma concentrations:

- i.) *For all pre-dose samples, the sampling time will be set to zero.*
- ii.) *For post-dose samples, the planned sampling time will be used in summary tables and the actual sampling times will be used for all figures of individual concentrations.*
- iii.) *All concentration values < lower limit of quantification (LLOQ) will be set to zero.*
- iv.) *Missing post-dose values will not be replaced.*

### Determination of PK metrics:

- i.) *For all pre-dose samples, the sampling time will be set to zero.*
- ii.) *For post-dose samples, the actual sampling time will be used.*
- iii.) *All pre-dose concentration values will be set to zero.*
- iv.) *Post-dose concentration values < LLOQ before  $t_{max}$  will be set to zero if there are no further concentrations > LLOQ at later time points.*
- v.) *Post-dose concentration values < LLOQ before  $t_{max}$  will be set to the lower limit of quantitation if there are further concentrations > LLOQ at later time points.*
- vi.) *Post-dose concentration values < LLOQ after  $t_{max}$  will be ignored if there are no further concentrations > LLOQ at later time points.*
- vii.) *Post-dose concentration values < LLOQ after  $t_{max}$  will be ignored if there are further concentrations > LLOQ at later time points.*
- viii.) *Missing post-dose values will not be replaced.*

PK metrics will be determined by Synteract. Plasma concentration data will be transferred from an external laboratory (York Bioanalytical Solutions (YBS), MLM laboratories) to Synteract as detailed in separate data transfer specifications.

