7.4 Investigational medicinal product(s)

7.4.1 Identity of investigational medicinal product(s)

The identity of the investigation products is summarized in Table 7-1.

Table 7-1: Identity of Investigational Products

	Test product	Placebo	Reference product
Name	Dasiglucagon	Placebo	GlucaGen®
Active substance	ZP4207	Not applicable	Recombinant glucagon hydrochloride
Formulation	Liquid formulation, 0.6 mL	Liquid formulation, 0.6 mL	Powder and solvent for reconstitution as 1 mL solution for injection
Strength	1 mg/mL	Not applicable	1 mg/mL
Container	Single use pre-filled syringe	Single use pre-filled syringe	Powder and solvent for reconstitution packed together in a plastic box. A "hypo-kit"
Manufacturer	Zealand Pharma A/S, Glostrup (Copenhagen), Denmark	Zealand Pharma A/S, Glostrup (Copenhagen), Denmark	Novo Nordisk A/S, Bagsværd, Denmark
Storage requirements	Store between 2 and 8°C	Store between 2 and 8°C	Store between 2 and 8°C

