5.1 Background of the trial

Hypoglycemia

Hypoglycemia in patients with diabetes is defined as episodes of an abnormally low plasma glucose concentration.⁹ This is a common, unpredictable, and potentially dangerous side effect of treatment of diabetes mellitus with especially insulin or sulfonylureas. It is more frequent in patients with profound endogenous insulin deficiency, such as occurs in type 1 diabetes mellitus (T1DM) and advanced type 2 diabetes mellitus. Treatment of type 2 diabetes mellitus with insulin causes hypoglycemia progressively and more frequently over time, whereas in T1DM, hypoglycemia is experienced throughout the course of established disease.

Symptoms and signs of hypoglycemia are not specific. Patients undergoing a hypoglycemic episode experience unpleasant symptoms such as anxiety, sweating, hunger, tremors, palpitations, paresthesia, nausea and pallor. Depending on its severity, the hypoglycemia may lead to mild confusion, behavioral changes, loss of consciousness, seizures, coma, and death.¹

The incidence of hypoglycemic events or even the fear of hypoglycemia influences patients' adherence to prescribed treatment regimens for diabetes mellitus. This leads to inadequate glycemic control, which in turn may lead to an increased risk of diabetic complications.

Glucagon

Glucagon is a naturally occurring hormone, secreted from the alpha cells of the pancreatic islets. Glucagon plays a central role in the regulation of glucose homeostasis and is the counterpart of insulin for controlling blood glucose levels (i.e. it acts in opposition to insulin in terms of effects on blood glucose levels). Glucagon stimulates hepatic glycogenolysis and gluconeogenesis in hypoglycemic states, thereby restoring glucose homeostasis. Glucagon receptor agonism has also been shown to exert effects on lipid metabolism, energy balance, body adipose tissue mass and food intake.

Insulin decreases blood glucose levels and cases of hypoglycemia can be reversed by glucagon. Therefore, glucagon is indicated for the treatment of severe hypoglycemia.

Dasiglucagon

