### Summary statistics of plasma concentration table:

Summary statistics of the plasma concentration by treatment group and time point will be presented. In addition, the change from pre-dose will be summarized. Results will be displayed using 3 significant digits.

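### The SAP specifies no correction for the child's own glucagon in the GlucaGen PK metrics, so GlucaGen half-life and volume can be overstated by an amount the documents do not let us fix

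*SAP*

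**What the plan says.** SAP 12.1, under the rules for determining PK metrics, states "All pre-dose concentration values will be set to zero". This covers quantifiable values as well as those below LLOQ. The remaining rules deal only with sampling times, values below LLOQ and missing values ("Missing post-dose values will not be replaced"). A value below LLOQ after tmax "will be ignored if there are no further concentrations > LLOQ at later time points", and it is likewise ignored if quantifiable values follow. No rule removes the pre-dose level from post-dose values.

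Elsewhere the measured pre-dose value is kept. SAP 12.2 lists the change from pre-dose for each child, and for the concentration table it says "In addition, the change from pre-dose will be summarized".

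SAP 12.1 says that plasma dasiglucagon and GlucaGen "are determined at pre-dose, and at 10, 20, 30, 40, 60, 90, 140, 220, and 300 minutes after dosing". For lambda_z, SAP 12 specifies a log-linear fit to the terminal linear portion and adds "At least 3 concentrations in the terminal elimination phase will be required to calculate" it. It does not say how the points are chosen.

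Protocol 7.4.1 gives the active substance of GlucaGen as "Recombinant glucagon hydrochloride". Protocol 5.1 states "Glucagon is a naturally occurring hormone, secreted from the alpha cells of the pancreatic islets". The metrics are listed as PK endpoints for both products (Protocol 6 and 10.1.5), and Table 14.4.1.2 shows the two products side by side.

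**The concern.** A GlucaGen sample measures injected glucagon plus whatever the child secretes. Subtracting the pre-dose level is the usual way to separate the two. Here that level is measured and used in one table, but dropped from the metrics while it remains inside every post-dose value.

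This matters most in the tail. Injected drug falls away within a few hours, while a steady endogenous level does not. A log-linear fit through late samples then partly describes a plateau. The fitted lambda_z is too small, so half-life and Vz/f rise; AUC0-inf and MRT also rise, and CL/f falls. A reader comparing the two columns of Table 14.4.1.2 could take this artefact for a pharmacological difference between the products.

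**Working it through.** The documents state no GlucaGen half-life, Vz/f, MRT, endogenous level or LLOQ, so there is no planned figure to reproduce. The check is a sensitivity calculation.

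**Inputs from the documents.** Sampling times are those in SAP 12.1. GlucaGen tmax is 20 min (Protocol 5.1, adult data).

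**Assumed inputs.** One compartment with first-order absorption. True half-life 20 or 28 min; Protocol 5.1 gives 28 min, but for dasiglucagon. A constant endogenous level E of 0.1% to 2% of Cmax is added to every post-dose value, and the pre-dose value is set to zero.

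**Model.** C(t) is proportional to exp(−kt) − exp(−ka·t), with k = ln 2 / half-life and ka chosen so that ln(ka/k)/(ka − k) = 20 min. For a 20 min half-life, ka = 2k and C(t)/Cmax = 4[exp(−kt) − exp(−2kt)]. For 28 min, the absorption half-life is 7.8 min.

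**Injected drug left, as % of Cmax.** At 140, 220 and 300 min: 3.10, 0.195 and 0.012 (20 min half-life); 7.12, 0.98 and 0.14 (28 min). With E = 1%, injected drug is therefore 16% or 50% of the measured value at 220 min, and 1% or 12% at 300 min.

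**Half-life from the last three samples.** These times are equally spaced, so the slope is [ln C(300) − ln C(140)]/160. With a 20 min half-life and E = 1%, the measured values are 4.101, 1.195 and 1.012. The slope is (0.0119 − 1.4112)/160 = −0.00875 per min, and ln 2/0.00875 gives about 79 min.

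Apparent half-life (min) by fitting window:

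| E, % of Cmax | True 20: last 3 | last 5 | 60–140 min | True 28: last 3 | last 5 | 60–140 min |
|---|---|---|---|---|---|---|
| 0 | 20.0 | 20.3 | 20.9 | 28.0 | 28.1 | 28.3 |
| 0.1 | 33.1 | 27.0 | 21.1 | 32.4 | 30.7 | 28.5 |
| 0.5 | 56.9 | 36.3 | 22.1 | 44.6 | 37.2 | 29.2 |
| 1 | 79.3 | 43.4 | 23.2 | 56.4 | 42.8 | 30.1 |
| 2 | 119.2 | 53.8 | 25.4 | 76.4 | 51.3 | 31.8 |

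**Other metrics, last-three fit, E from 0.1% to 2%.** AUC0-inf is taken as AUClast + Clast/lambda_z. (The bracketing printed in SAP 12 divides the whole sum by lambda_z; that needs separate correction.) Vz/f = Dose/(lambda_z × AUC0-inf), MRT = AUMCinf/AUC0-inf and CL/f = Dose/AUC0-inf. Ratios to the values without endogenous glucagon:

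- half-life 1.16 to 5.95
- Vz/f 1.15 to 5.06
- MRT 1.02 to 1.74
- AUC0-inf 1.01 to 1.18
- CL/f 0.99 down to 0.85

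**The zeroing rule alone.** It affects only the first trapezoid. At E = 1% of Cmax that is 0.01 × 10/2 = 0.05 Cmax·min, against an AUC of about 56 Cmax·min, or roughly 0.1%. It does not enter lambda_z.

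**If LLOQ is 20% above E.** Some late samples drop out, and the last-three half-life ratio becomes 1.11 to 1.60. It does not shrink in every case: with a 28 min half-life and E of 0.1% or 0.5%, drug plus endogenous glucagon still exceeds LLOQ at 300 min, so nothing is dropped.

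**With the correction.** If E is constant, subtracting it restores the clean values: for an assumed 20 min half-life, 20.0 min from the last three samples and an MRT of 44.3 min.

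**The case against.** The strongest reply is that the size is unknown and the SAP already limits the problem. Values below LLOQ after tmax are ignored, so a low endogenous level may never reach the fit. The SAP fits the terminal elimination phase, and an analyst who recognises a plateau need not use it; with the 60, 90 and 140 min samples the bias is small. The metrics are descriptive, the PK objective names dasiglucagon, and change from pre-dose is reported anyway. A single pre-dose value is also an imperfect baseline: it is drawn during induced hypoglycemia, and food is allowed after 60 minutes (Protocol 7.4.5.2.2).

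Most of this stands, and it limits the point to a clarification. It does not remove it. The choice of points is left open, so the reported half-life depends on an unstated decision. The change-from-pre-dose table does not feed the metrics. An approximate baseline is a reason to show both versions, not to omit the correction.

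A reader might infer that the late GlucaGen samples do measure endogenous hormone and that half-life, volume and MRT are all badly overstated. The documents do not support that: it needs the endogenous level, Cmax, half-life and LLOQ, and MRT moves by only 2% at E = 0.1%. Nor do they support blaming the zeroing rule, or asserting that dasiglucagon is unaffected. Protocol 7.4.10 matches the assay to the product given, but does not say whether the dasiglucagon assay also detects native glucagon.

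**Conclusion.** The gap is real: the SAP specifies no baseline correction for an analyte that is also endogenous, and no window for lambda_z. The direction follows whenever endogenous glucagon is quantifiable. Half-life, Vz/f, MRT and AUC0-inf are biased upward and CL/f downward.

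The size is conditional. Under the stated assumptions half-life can be overstated 1.2- to 6-fold if the last three samples are used, but only slightly if the 60–140 min samples are. Vz/f follows half-life closely; MRT, AUC0-inf and CL/f are less sensitive. The bias is generally smaller if the endogenous level lies below LLOQ. All these figures rest on a constant endogenous level and on half-lives and levels that the documents do not supply for GlucaGen in children. The consequence is confined to descriptive GlucaGen PK; the primary endpoint and the testing hierarchy are untouched.

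**What to change.** In SAP 12.1, for the GlucaGen arm:

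- Calculate the PK metrics from baseline-corrected concentrations: each post-dose value minus that child's own pre-dose value. Set corrected values at or below zero to zero for AUC, and leave them out of the lambda_z regression.
- Show the uncorrected metrics beside the corrected ones.
- Report the pre-dose concentrations and the assay LLOQ.
- Predefine the lambda_z window, or the rule that selects it, before unblinding.
- State that one pre-dose value is an approximate correction, because induced hypoglycemia and the meal allowed after 60 minutes may shift endogenous glucagon.

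The pre-dose samples are already planned, so no extra blood is needed. The cost is a few data-handling rules, including how the correction works alongside the LLOQ rules, and one additional block of output. Some children may have too few positive corrected values for lambda_z under the three-point requirement; report how many.
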